3.3 Inclusion of Women and Minorities

NIH policy requires that women and members of minority groups and their subpopulations be included in all NIH-supported biomedical and behavioral research projects involving NIH-defined clinical research unless a clear and compelling rationale and justification establishes to the satisfaction of the funding Institute & Center (IC) Director that inclusion is inappropriate with respect to the health of the subjects or the purpose of the research. Exclusion under other circumstances must be designated by the Director, NIH, upon the recommendation of an IC Director based on a compelling rationale and justification. Cost is not an acceptable reason for exclusion except when the study would duplicate data from other sources. Women of childbearing potential should not be routinely excluded from participation in clinical research. Please see <http://grants.nih.gov/grants/funding/phs398/phs398.pdf>.

Epithelioid hemangioendothelioma is slightly more prevalent in females than males. There is no known predilection of the disease for a particular race or ethnic background. The study is open to eligible males and females of all races and ethnicity and enrollment will not discriminate on the basis of race or ethnicity. Because of the rarity of locally advanced or metastatic EHE and the need to complete accrual to the trial in a timely manner, patients will be enrolled as they consent and are determined to be eligible to participate. The study will not target enrollment to meet a predefined goal for accrual for any particular gender, race or ethnicity.

4. REGISTRATION PROCEDURES

4.1 Investigator and Research Associate Registration with CTEP

4.1.1 CTEP Registration Procedures

Food and Drug Administration (FDA) regulations and National Cancer Institute (NCI) policy require all investigators participating in any NCI-sponsored clinical trial to register and to renew their registration annually.

Registration requires the submission of:

- a completed ***Statement of Investigator Form*** (FDA Form 1572) with an original signature
- a current Curriculum Vitae (CV)
- a completed and signed ***Supplemental Investigator Data Form*** (IDF)
- a completed ***Financial Disclosure Form*** (FDF) with an original signature

Fillable PDF forms and additional information can be found on the CTEP website at http://ctep.cancer.gov/investigatorResources/investigator_registration.htm.

For questions about Investigator Registration, please contact the ***CTEP Investigator Registration Help Desk*** by email at [contact].

4.1.2 CTEP Associate Registration Procedures / CTEP-IAM Account

The Cancer Therapy Evaluation Program (CTEP) Identity and Access Management (IAM) application is a web-based application intended for use by both Investigators (*i.e.*, all physicians involved in the conduct of NCI-sponsored clinical trials) and Associates (*i.e.*, all staff involved in the conduct of NCI-sponsored clinical trials).

Associates will use the CTEP-IAM application to register (both initial registration and annual re-registration) with CTEP and to obtain a user account.

Investigators will use the CTEP-IAM application to obtain a user account only. (See CTEP Investigator Registration Procedures above for information on registering with CTEP as an Investigator, which must be completed before a CTEP-IAM account can be requested.)

An active CTEP-IAM user account is required to access all CTEP applications and, if applicable (*e.g.*, all Network trials), all Cancer Trials Support Unit (CTSU) applications and websites.

Additional information can be found on the CTEP website at http://ctep.cancer.gov/branches/pmb/associate_registration.htm.

For questions about Associate Registration or CTEP-IAM Account Creation, please contact the ***CTEP Associate Registration Help Desk*** by email at [contact].

4.2 Site Registration

This study is supported by the NCI Cancer Trials Support Unit (CTSU).

Each investigator or group of investigators at a clinical site must obtain Institutional Review Board (IRB) approval for this protocol and submit IRB approval and supporting documentation to the CTSU Regulatory Office before they can be approved to enroll patients. Assignment of site registration status in the CTSU Regulatory Support System (RS) uses extensive data to make a determination of whether a site has fulfilled all regulatory criteria including but not limited to: an active Federal Wide Assurance (FWA) number, an active roster affiliation with the Lead Network or a participating organization, a valid IRB approval, and compliance with all protocol specific requirements.

Sites participating on the NCI CIRB initiative that are approved by the CIRB for this study are not required to submit IRB approval documentation to the CTSU Regulatory Office. For sites using the CIRB, IRB approval information is received from the CIRB and applied to the RSS in an automated process. Signatory Institutions must submit a Study Specific Worksheet for Local Context (SSW) to the CIRB via IRBManager to indicate their intent to open the study locally. The CIRB's approval of the SSW is then communicated to the CTSU Regulatory Office. In order

for the SSW approval to the processed, the Signatory Institution must inform the CTSU which CIRB-approved institutions aligned with the Signatory Institution are participating in the study.

4.2.1 Downloading Regulatory Documents

Site registration forms may be downloaded from the *NCI protocol #10015* protocol page located on the CTSU Web site. Permission to view and download this protocol is restricted and is based on person and site roster data housed in the CTSU RSS. To participate, Investigators and Associates must be associated with the Corresponding or Participating protocol organization in the RSS.

- Go to <https://www.ctsu.org> and log in using your CTEP-IAM username and password.
- Click on the Protocols tab in the upper left of your screen.
- Either enter the protocol # in the search field at the top of the protocol tree, or click on the By Lead Organization folder to expand, then select *EDDO-MI014*, and protocol #10015.
- Click on LPO Documents, select the Site Registration documents link, and download and complete the forms provided. (Note: For sites under the CIRB initiative, IRB data will load to RSS as described above.)

4.2.2 Requirements For #10015 Site Registration:

- CTSU Transmittal Sheet (optional)
- IRB approval (For sites not participating via the NCI CIRB; local IRB documentation, and IRB-signed CTSU IRB Certification Form, Protocol of Human Subjects Assurance Identification/IRB Certification/Declaration of Exemption Form, or combination is accepted)

4.2.4 Checking Site Registration Status

You can verify your site registration status on the members' section of the CTSU website.

- Go to <https://www.ctsu.org> and log in to the members' area using your CTEP-IAM username and password.
- Click on the Regulatory tab at the top of your screen.
- Click on the Site Registration tab.
- Enter your 5-character CTEP Institution Code and click on Go.

Note: The status given only reflects compliance with RIB documentation and institutional compliance with protocol-specific requirements as outlined by the Lead Network. It does not reflect compliance with protocol requirements for individuals participating on the protocol or the enrolling investigator's status with the NCI or their affiliated networks.

4.3 Patient Registration

4.3.1 OPEN / IWRS

Patient enrollment will be facilitated using the Oncology Patient Enrollment Network (OPEN). OPEN is a web-based registration system available to users on a 24/7 basis. It is integrated with the CTSU Enterprise System for regulatory and roster data interchange and with the Theradex Interactive Web Response System (IWRS) for retrieval of patient registration/randomization assignment. Patient enrollment data entered by Registrars in OPEN / IWRS will automatically transfer to the NCI's clinical data management system, Medidata Rave.

The OPEN system will provide the site with a printable confirmation of registration and treatment information. Please print this confirmation for your records.

4.3.2 OPEN/IWRS User Requirements

OPEN/IWRS users must meet the following requirements:

- Have a valid CTEP-IAM account (*i.e.*, CTEP username and password).
- To enroll patients: Be on an ETCTN Corresponding or Participating Organization roster with the role of Registrar.
- Have regulatory approval for the conduct of the study at their site.

Prior to accessing OPEN/IWRS, site staff should verify the following:

- All eligibility criteria have been met within the protocol stated timeframes.
- If applicable, all patients have signed an appropriate consent form and HIPAA authorization form.

4.3.3 Patient Enrollment Instructions

The SARC Research Project Manager (RPM) must be notified before patients are consented and begin eligibility screening for enrollment in the study. The RPM may be notified by [contact], [contact], or email:

[contact]. The SARC RPM will inform the site if an enrollment slot is available based on the total number of patients with *TAZ-CAMTA1* gene fusion positive EHE enrolled in the trial. Patients must not be consented until the site has been informed that an enrollment slot is available. An enrollment slot will only be opened (made available) if a patient enrolled in the trial and started on trametinib does not have *TAZ-CAMTA1* gene fusion positive EHE confirmed after testing by FISH at the central/reference laboratory. After obtaining patient consent, the site should provide the SARC RPM the date informed consent was obtained, patient initials, patient age, and whether the patient has agreed to participate in the optional tumor biopsies for research. This information will be used by the SARC office to track enrollment and assist sites with shipment of the biologic samples for the correlative research studies.

4.4 General Guidelines

Following registration, patients should begin protocol treatment within 7 days. Issues that would cause treatment delays should be discussed with the Principal Investigator. If a patient does not receive protocol therapy following registration, the patient's registration on the study may be canceled. The Study Coordinator should be notified of cancellations as soon as possible.

5. TREATMENT PLAN

5.1 Agent Administration

Treatment will be administered on an outpatient basis. Reported adverse events and potential risks are described in Section 7. Appropriate dose modifications are described in Section 6. No investigational or commercial agents or therapies other than those described below may be administered with the intent to treat the patient's malignancy.

5.1.1 Trametinib

Trametinib 2 mg will be taken orally once daily with a cycle length of 28 days. The effect of food on trametinib absorption is unknown. The current recommendation is to administer trametinib on an empty stomach, 1 hour before or 2 hours after a meal; the recommendation to administer trametinib on an empty stomach may change based on

emerging data. Patients will be instructed to take the medication at approximately the same time each day with a full glass of water. If a dose is missed, the patient will be instructed to take it as soon as they remember. If the next scheduled dose is within 12 hours, they will skip the missed dose. The patient will be requested to maintain a medication diary of each dose of medication. The medication diary should be returned to and/or reviewed by clinic staff at each scheduled clinic visit during the course of treatment.

Regimen Description					
Agent	Premedication; Precautions	Dose	Route	Schedule	Cycle Length
Trametinib	Take 1 or more hours before or 2 or more hours after food. Take with at least 8 ounces of water	2 mg	PO	once daily	28 days (4 weeks)

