2.2.1.2 Clinical Pharmacokinetics (PK) and Activity of Trametinib

FTIH Phase 1 Trial of Trametinib Monotherapy (MEK111054)

There are 3 parts in this study. Part 1: The dose-escalation portion involves administration of trametinib (repeat doses of 0.125 mg to 4.0 mg) to patients with solid tumors or lymphoma in one of three schedules - (1) QD for 21 days followed by 7 days without drug, (2) loading dose on Day 1 or Day 1-2, followed by QD with the designated dose, or (3) QD dosing without a drug holiday. Part 2: cohort expansion at the recommended phase 2 dose (RP2D) for pancreatic cancer, melanoma, non-small cell lung cancer (NSCLC), colorectal cancer (CRC), or any BRAF mutation-positive cancer. Part 3: expansion to characterize the biologically active range of trametinib via analysis of pharmacodynamic biomarkers (biopsies or FDG-PET).

The MTD of trametinib was established as 3 mg QD, but the recommended phase 2 dose (RP2D) was chosen at 2 mg QD based on tolerability of repeated cycles (Infante *et al.*, 2010).

Trametinib treatment in children

A 3 part phase 1/2, open-label, multicenter study of trametinib in pediatric subjects with recurrent or refractory tumors (NCT02124772) is underway. Unpublished results from the part A, dose escalation portion of the study which included 38 subjects is complete. The recommended phase 2 dose in children 6 years of age or older is 0.025 mg/kg per day with the total dose not to exceed 2 mg per day. A dose of 0.04 mg/kg per day (corresponding to a dose of 2 mg per day in a subject weighing 50 kg) was associated with skin related dose-limiting toxicities. Pharmacokinetic steady state drug concentration target was met in children 6 years of age or older using a dose of 0.025 mg/kg per day. (confidential information from Novartis)

PK and metabolism of trametinib:

PK measurements were conducted under fasting conditions. After a single dose (Day 1), AUC_{0-24} and C_{max} values were dose-proportional up to 6 mg, lower than dose proportional following 8 mg, and greater than dose proportional following the 10 mg dose. Median T_{max} was 1.5 hours.

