In a phase 1/2 monotherapy study, acute myeloid leukemia (AML) or myelodysplastic syndrome (MDS) patients were given trametinib at dose levels from 1-2 mg QD. Drug-related AEs in 45 patients were similar to that observed in patients with solid tumors, and 2 mg PO QD was selected for further investigation in this patient population. Twelve patients (23%) withdrew due to an AE, including cardiac failure (2) and infection (2). Efficacy was reported in 39 patients (Borthakur *et al.*, 2010). The best response in 13 patients with KRAS or NRAS mutations included 3 CRs (23%), 7 SD (54%), and 1 PD (progressive disease) (5%). In 26 patients with wild-type RAS or an unknown mutation, there were 2 PRs (8%).

In a multicenter phase 2 study, NSCLC patients with KRAS mutant tumors were randomized 2:1 to receive trametinib (2 mg QD) or docetaxel (75 mg/m² IV every 3 weeks) (Blumenschein *et al.*, 2013). A total of 134 pts were randomized to trametinib (89) or docetaxel (45); 129 patients had KRAS-mutant NSCLC. The hazard ratio for PFS was 1.14 (95% CI, 0.75-1.75; *P*=0.5197) with a median PFS of 11.7 versus 11.4 weeks for trametinib versus docetaxel. The overall response rate (ORR) was 12% for trametinib and 12% for docetaxel.

In a double-blind, phase 2 study evaluating the combination of gemcitabine with trametinib, untreated pancreatic cancer patients were randomized to receive gemcitabine (1000 mg/m² weekly \times 7 for 8 weeks, then weekly \times 3 every 4 weeks) plus either trametinib 2mg or placebo QD (Infante *et al.*, 2013). Median OS was 8.4 months with trametinib compared to 6.7 months with placebo. Median PFS was 16 weeks versus 15 weeks, and ORRs and median duration of responses were 22% and 23.9 weeks and 18% and 16.1 weeks on trametinib and placebo; the median OS and ORR in the subgroup of patients with KRAS mutations (143/160) was similar to OS and ORR for all randomized patients.

Trametinib has not been formally evaluated in patients with EHE or soft tissue sarcoma. We do not expect drug pharmacokinetics or adverse events rates to differ significantly from the experience of trametinib in treatment of metastatic melanoma or non-small cell lung cancer.

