3. PATIENT SELECTION

3.1 Eligibility Criteria

- 3.1.1 Patients must have measurable disease, defined as at least one lesion that can be accurately measured in at least one dimension (longest diameter to be recorded for non-nodal lesions and short axis for nodal lesions) as ≥ 20 mm (≥ 2 cm) with conventional techniques or as ≥ 10 mm (≥ 1 cm) with spiral CT scan, MRI, or calipers by clinical exam. Baseline imaging must be obtained within 30 days of Day 1 of study. See Section 11 for the evaluation of measurable disease.
- 3.1.2 Patients must have histologically confirmed epithelioid hemangioendothelioma which is metastatic or locally advanced (unresectable), and tumor tissue (paraffin-embedded tissue block or tumor tissue on unstained glass slides) available for fusion FISH analysis at Cleveland Clinic. Patient tumor tissue stored in pathology archives may be used for fusion FISH; a new biopsy is not mandatory.

- 3.1.3 Patients must have evidence of disease progression per RECIST1.1 prior to enrollment or have evidence of cancer-related pain requiring symptom management with narcotic analgesics.
- 3.1.4 Because there is no established standard or approved drug therapy for treatment of EHE, patients previously untreated or treated with drug therapy for EHE are eligible. There is no limit on the number of prior regimens used to be eligible.
- 3.1.5 Age ≥ 15 years. EHE is very unlikely to arise before the age of 15 years.
- 3.1.6 ECOG performance status ≤ 2 (Karnofsky $\geq 60\%$, see Appendix A).
- 3.1.7 Life expectancy of greater than 6 months.
- 3.1.8 Able to swallow orally-administered medication and does not have any clinically significant gastrointestinal abnormalities that may alter absorption such as malabsorption syndrome or major resection of the stomach or small bowel.
- 3.1.9 All prior treatment-related toxicities must be CTCAE v5 grade ≤ 1 (**except alopecia**) at the time of enrollment.
- 3.1.10 Patients must have normal organ and marrow function as defined below within 2 weeks of patient registration (for blood results) and 30 days of registration for LVEF assessment:
 - Absolute neutrophil count (ANC) $\geq 1 \times 10^9/L$
 - Hemoglobin ≥ 9 g/dL, patients may receive transfusion to meet criterion
 - Platelets $\geq 75 \times 10^9/L$
 - Albumin ≥ 2.5 g/dL

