6. DOSING DELAYS/DOSE MODIFICATIONS

6.1 Trametinib Dose Modifications

The table below outlines the dose levels to be used for any necessary trametinib dose modifications:

Dose Level	Trametinib Dose/Schedule
0	2 mg once daily
-1	1.5 mg once daily
-2	1 mg once daily

A maximum of two trametinib dose level reductions are allowed. If a third dose level reduction is required, treatment will be permanently discontinued.

If a dose reduction of trametinib is required, but the toxicity resolves and no additional toxicities are seen after two cycles of treatment, the dose of trametinib may be re-escalated but should not exceed 2 mg once a day.

Dose modification and AE guidelines are outlined in the sections below for AEs that are deemed possibly related to trametinib:

- AEs not otherwise specified
- Rash
- Visual changes
- Diarrhea
- Liver chemistry elevation
- Ejection fraction changes
- Hypertension
- Prolonged QTc
- Pneumonitis

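### Patients aged 15–17 who weigh 50 kg or less start at a flat 2 mg, at or above the mg/kg dose that the protocol links to skin dose-limiting toxicities in children, with no reason given

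*Combined protocol and SAP*

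**What the plan says.** **Starting dose.** Section 5.1.1 states: "Trametinib 2 mg will be taken orally once daily with a cycle length of 28 days". Dose level 0 in section 6.1 is the same flat 2 mg, with levels of 1.5 mg and 1 mg below it. That section adds: "A maximum of two trametinib dose level reductions are allowed". After a reduction and recovery, "the dose of trametinib may be re-escalated but should not exceed 2 mg once a day". Neither age nor weight enters the dosing rules.

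**Who is admitted.** Sections 3.1 and 13.2 set the minimum age at 15. The remark attached to the age criterion is epidemiological: "EHE is very unlikely to arise before the age of 15 years". Sections 3.1 and 3.2 contain no weight criterion. The drug diary in Appendix D is worded for a parent as well as a patient, so minors are expected.

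**What the background reports for children.** Section 2.2.1.2 summarises an unpublished dose escalation in 38 paediatric subjects. It says: "The recommended phase 2 dose in children 6 years of age or older is 0.025 mg/kg per day", with a ceiling of 2 mg per day. It also says: "Pharmacokinetic steady state drug concentration target was met in children 6 years of age or older using a dose of 0.025 mg/kg per day". On the higher dose of 0.04 mg/kg per day it reads: "corresponding to a dose of 2 mg per day in a subject weighing 50 kg) was associated with skin related dose-limiting toxicities".

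**The nearest bridging statement.** The same section says: "We do not expect drug pharmacokinetics or adverse events rates to differ significantly from the experience of trametinib in treatment of metastatic melanoma", and it also names non-small cell lung cancer. It does not mention age or weight.

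**The concern.** The protocol reports a paediatric dose linked to dose-limiting toxicity and converts it to this trial's own dose at 50 kg. It then starts any 15–17-year-old of that weight or less at or above it, without comment. The adult basis for 2 mg (tolerability of repeated cycles in the first-in-human trial) and the lower paediatric recommendation stand in the same section, and nothing says which governs a minor.

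What is at stake is the early skin tolerability of a few small adolescents. Dose reductions act only after toxicity has appeared, and they do so slowly. Section 2.2.1.2 gives an effective half-life of about 4.5 days. In the randomised melanoma trial described in section 2.2.1.3, skin toxicity took a median of 48 days to resolve.

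**Working it through.** **Inputs**
- Flat dose levels of 2, 1.5 and 1 mg per day (section 6.1).
- Paediatric dose linked to skin dose-limiting toxicity: 0.04 mg/kg per day (section 2.2.1.2).
- Paediatric recommended dose: 0.025 mg/kg per day, maximum 2 mg (section 2.2.1.2).
- Body weights of 40, 45, 50 and 55 kg. These are illustrative assumptions, because the documents give neither the weights nor the number of minors.

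**Step 1: the plan's own conversion.** 0.04 mg/kg × 50 kg = 2.0 mg. This reproduces the figure in section 2.2.1.2.

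**Step 2: flat 2 mg expressed per kg.** Dose per kg = 2 / weight. The recommended paediatric dose in mg is the smaller of 2 and 0.025 × weight.

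| Weight | 2 mg in mg/kg | Multiple of 0.04 | Recommended dose | 2 mg as a multiple of it |
|---|---|---|---|---|
| 55 kg | 0.0364 | 0.91 | 1.375 mg | 1.45 |
| 50 kg | 0.0400 | 1.00 | 1.25 mg | 1.60 |
| 45 kg | 0.0444 | 1.11 | 1.125 mg | 1.78 |
| 40 kg | 0.0500 | 1.25 | 1.0 mg | 2.00 |

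The crossing point is 2 / 0.04 = 50 kg. At or below it, every patient is at or above 0.04 mg/kg and at 1.6 times the recommended dose or more.

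**Step 3: which existing level would serve as a lower start.** Three conditions seem reasonable: below 0.04 mg/kg, not below 0.025 mg/kg (where the concentration target was met), and at least one reduction left. The third matters because section 6.1.2 requires a one-level reduction for grade 2 rash, and for grade 1 rash not back to baseline in 2 weeks.

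| Start | mg/kg at 50 / 45 / 40 kg | Weight at which it equals 0.04 mg/kg | Reductions left |
|---|---|---|---|
| 2 mg | 0.0400 / 0.0444 / 0.0500 | 50 kg | 2 |
| 1.5 mg | 0.0300 / 0.0333 / 0.0375 | 37.5 kg | 1 |
| 1 mg | 0.0200 / 0.0222 / 0.0250 | 25 kg | 0 |

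Above 37.5 kg and up to 50 kg, 2 mg fails the first condition. A 1 mg start fails the third, and above 40 kg (1 / 0.025) it fails the second as well. The 1.5 mg level meets all three, at 1.20, 1.33 and 1.50 times 0.025 mg/kg for 50, 45 and 40 kg. At 37.5 kg or less, 1.5 mg is itself at or above 0.04 mg/kg (0.0429 at 35 kg), so those patients need an individual decision.

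**The case against.** **The evidence may not carry to ages 15–17.** The paediatric summary gives no ages, weights, counts or grades for the skin toxicities. Dose per kg is also not exposure: section 2.2.1.2 reports between-subject AUC variability of 20–41%. This stands, and it keeps the point minor.

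**Adults of the same size get the same mg/kg.** The adult maximum tolerated dose was a flat 3 mg, which is 3 / 50 = 0.06 mg/kg at 50 kg, so 0.04 mg/kg is not a general toxicity threshold. That is fair as far as it goes. But section 2.2.1.2 gives adults and children separate recommendations. The paediatric one has a 2 mg ceiling that is reached only at 2 / 0.025 = 80 kg, so it is not confined to small children. Whether a light 16-year-old resembles a child or an adult is the question left open.

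**The toxicity is already managed.** Section 6.1.2 calls for topical steroids and antibiotics from Day 1, with prophylaxis recommended for 6 weeks, and section 10 schedules physical examinations in weeks 1, 3 and 5. This is a real partial mitigation, but it applies to everyone and does not bear on the choice of starting dose.

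**A 1.5 mg rule is not well supported either.** It falls between the two doses that the summary describes. At 38 kg it is 1.5 / 38 = 0.0395 mg/kg, close to the dose it is meant to avoid. A minor of 51 kg would stay on 2 / 51 = 0.0392 mg/kg. These points justify having clinicians confirm the level. They do not remove the benefit, since the rule still lowers the dose for those at 50 kg or less.

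**Conclusion.** The point holds as a minor safety issue. Patients aged 15–17 who weigh 50 kg or less start at 0.040 mg/kg or more, at or above the paediatric dose linked to skin dose-limiting toxicity and at 1.6 times the recommended paediatric dose or more. The documents do not justify this.

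The conclusion rests on the section 2.2.1.2 summary being informative at these ages, which is an inference. The number affected may be zero: the trial seeks 27 fusion-positive patients with a disease that peaks in adulthood.

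Three stronger readings are tempting and should not be drawn:
- **That adolescents are shown to be at excess risk, or are overdosed.** No adolescent toxicity or exposure data are given.
- **That every minor below 80 kg is affected.** Flat 2 mg does exceed 0.025 mg/kg up to 80 kg, but above 50 kg it is below the dose linked to toxicity, and the summary does not describe doses in between.
- **That the efficacy result is compromised.** Section 13.5.2 keeps eligible patients who took at least one dose in the main response analysis, and no effect on error rates follows.

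**What to change.** For remaining enrolment, add to section 5.1.1:

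> Patients aged 15–17 who weigh 50 kg or less at baseline start at dose level -1 (1.5 mg once daily). If weight is 37.5 kg or less, the starting dose is agreed with the CTEP Medical Monitor before registration. All other patients start at 2 mg.

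Add to section 6.1:

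> A patient who starts at 1.5 mg has one dose reduction, to 1 mg, and is not re-escalated above 1.5 mg.

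The second addition is needed because section 6.1 now permits re-escalation up to 2 mg. The sponsor's clinicians should confirm the 1.5 mg level before it is adopted, using any adolescent pharmacokinetic and safety data they hold at these weights.

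**Cost.** The change needs protocol and consent wording only. The 1.5 mg level exists (section 6.1), 0.5 mg tablets are supplied (section 8.1.1), the diary already lists 1.5 mg (Appendix D), and weight is measured before the study (section 10). The response analysis set is unchanged.

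**Downside.** These patients have one reduction instead of two. From 1.5 mg, the first reduction leads to 1 mg and treatment continues. A second, with the first not reversed, ends treatment, where a 2 mg start would allow one more step. The lowest dose, 1 mg, is the same under both plans.
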